8.3.1 BGB324 and erlotinib dose levels

The dose of BGB324 will be escalated following a standard 3+3 design in combination with erlotinib. The starting dose level of Arm A (600 mg loading dose administered over 2 days with a 200 mg daily) was selected based on the results of PK modelling.

The total loading dose may be given over 2 days (Days 1 and 2) or 3 days (Days 1, 2, and 3)*. Possible dosing levels are illustrated in Table 4 also describes the maximum dose escalation step for any increase in loading or daily dose. Note that although the half-life of BGB324 has resulted in the recommendation to give a BGB324 loading dose over 2 days to achieve steady state by Day 4, the use of the loading dose will depend on tolerability and DLT evaluation, and the SMC may recommend the dose is reduced. This may be achieved by giving the total loading dose over 3 days, giving a lower (including intermediate) loading dose, or not giving a loading dose at all.

* At the time of Amendment 5 a 3 day loading dose schedule has been confirmed

In Arm A, at least 3 evaluable patients will be entered per dose cohort according to the 3+3 study design as described below. A dose cohort will include at least 3 patients on the same loading dose schedule and daily dose level.

The SMC may consider that data from 3 patients at any dose level is sufficient to confirm the RP2D. In addition, the SMC may recommend that alternative dose levels or dosing schedules are explored as part of the study. At the time of patient registration, the loading dose schedule, loading dose and daily dose will be confirmed.

Table 4 Possible BGB324 Dosing Levels Involving A Loading Dose and Daily Dose

Total Loading Dose (mg)	Day 1 and 2 Loading Dose (mg)	Days 1, 2 and 3 Loading Dose (mg)	Daily Dose (mg)
600	--	200	100
800	400	--	100
1200	600	400	200

If 2 DLTs occur in the combination treatment at the Arm A BGB324 starting dose, a lower dose level may be investigated (see Section 8.3.2)

If a patient withdraws or is withdrawn for reasons other than DLT prior to completing Cycle 1, the patient will be replaced for the purposes of toxicity evaluation. Patients who experience a DLT during Cycle 1 may continue on BGB324 treatment (at their assigned daily dose or lower).

In Arm A the starting erlotinib dose will be 150 mg daily during the first continuous 21-day treatment cycle. Patients who require an erlotinib dose reduction prior to completing 1 cycle of treatment will not be evaluable for toxicity and may be replaced. After completion of Cycle 1 the daily dose of erlotinib may be reduced in accordance with the patient prescribing information. In response to potential toxicity the SMC may recommended evaluating lower doses of erlotinib.

The prescribing information for erlotinib recommends a 150mg dose for NSCLC patients, however if local clinical judgement/standards require, a patient in Arm B or C may be treated at a lower erlotinib dose (i.e., 100 mg).

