STUDY DRUG DOSE, SCHEDULE, ROUTE of ADMINISTRATION	
In the Run-in Cohort, BGB324 will be administered as a single agent. In Arms A, B, and C, BGB324 will be administered in combination with erlotinib. At the time of

	
Amendment 5 the Run in Cohort and Arm A have completed recruitment.
 
BGB324
 
BGB324 is prepared in size zero capsules each containing 100 mg of drug substance for oral administration.
 
BGB324 will be self-administered orally on an empty stomach according to a daily schedule during continuous 21-day treatment cycles. In Cycle 1, a loading dose of BGB324 may be administered followed by smaller daily dose (see Table 4).
 
Dose escalation can only occur in Arm A. If unacceptable toxicity is reported, the Sponsor and Investigators may agree to implement a lower dose for investigation or other dosing schedules.
 
In Arms B and C, BGB324 will be administered at the RP2D (the dose identified in Arm A that can be safely administered in combination with erlotinib).

	
Erlotinib
 
Erlotinib will be self-administered orally on an empty stomach according to a daily schedule during continuous 21-day treatment cycles in Arms A, B, and C.
 
The starting erlotinib dose in Arm A will be 150 mg daily. Patients requiring a dose reduction before the end of Cycle 1 will not be evaluable for toxicity and may be replaced.
 
The prescribing information for erlotinib recommends a 150mg dose for NSCLC patients, however if local clinical judgement/standards require, a patient in Arm B or C may be treated at a lower erlotinib dose (i.e., 100 mg).
 
If a patient presents with erlotinib toxicities that warrant dose reduction, the dose may be reduced in accordance with the current prescribing information. If the patient is required to cease treatment with erlotinib due to toxicity, they should either be withdrawn from the study or allowed to continue receiving BGB324 as a single agent until disease progression (unless unacceptable toxicity, death or withdrawal of consent).
 
Both drugs will be taken with water in the morning on a fasted stomach. BGB324 should be administered in the hour following erlotinib administration and at least 2 hours before breakfast (except on those days when the patient attends the clinic).

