8.3.2 Dose escalation scheme

In Arm A, initially 3 patients will be recruited at a starting dose of 600 mg on Days 1 and 2 followed by 200 mg daily, and must complete 1 21-day cycle of treatment before a dose evaluation is made. A patient must receive all loading doses and miss no more than 3 daily doses in Cycle 1 to be considered as informative to support dose escalation, unless the inability to administer BGB324 was a result of treatment-related toxicity.

[figure not shown]
If 1 patient in a cohort experiences a DLT during Cycle 1, the cohort will be expanded to 6 patients. If 2 of 3 or 2 of 6 patients in a cohort experience DLT, no further dose-escalation will take place and the prior dose level will be nominated as the RP2D.

Safety reviews and recommendations for dose escalation or reduction will be made by the SMC. Minutes of the SMC meetings will be placed in the Trial Master File. The decision to dose escalate will be based on the safety and tolerability of BGB324 in combination with erlotinib observed in the first cycle of treatment.

If dose escalation occurs, 3 patients will be recruited at Dose Level 2 and will complete 1 cycle of treatment before a dose escalation evaluation is made, as outlined above.

Dose escalation may be stopped prior to achieving the MTD if it is considered by the Sponsor and SMC that a clinically acceptable RP2D has been achieved. If the starting dose exceeds the MTD, a lower dose, or dosing schedule (including an extended loading dose schedule) may be explored if recommended by the SMC.

If a patient withdraws or is withdrawn for reasons other than DLT prior to completing Cycle 1, the patient will be replaced for the purposes of evaluation of BGB324 dose. The operating characteristics of the 3+3 dose escalation process are summarized in Figure 8.

Figure 8 Operating Characteristics of the 3+3 Dose Escalation Process

Abbreviations: DLT=dose limiting toxicity; MTD=maximum tolerated dose

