8.3.3 Assessment of DLTs

AEs will be assessed using the National Cancer Institute (NCI) CTCAE Version 4.03 (See Appendix 4) during the first cycle (21 days) of treatment in Arm A for the purposes of establishing the dose of BGB324 that can be safely given in combination with erlotinib.

DLTs will include:

- Any non-hematological toxicity \geq Grade 3, except Grade 3 nausea, vomiting or diarrhea that resolves within 72 hours with optimal therapy.
- Grade 4 thrombocytopenia or Grade 3 thrombocytopenia with bleeding.
- Grade 4 neutropenia persisting for \geq 5 days or Grade 3 or 4 febrile neutropenia.
- Treatment discontinuation or dose reduction for >72 hours during the first cycle as a result of treatment-related toxicity.

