11.7 Patient Replacement

Patients in Arm A who discontinue during the DLT assessment period (Cycle 1 [21 days]) for any reason other than a DLT will be replaced. All other patients who discontinue study treatment will not be replaced.

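### Arm A DLTs are tabulated over the whole Safety Population, which can dilute the DLT rate and does not show whom Protocol 8.3.1 removed from the escalation count

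*Protocol*

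**What the plan says.** **Who counts for escalation.** Protocol 8.3.1 builds the 3+3 on evaluable patients: "In Arm A, at least 3 evaluable patients will be entered per dose cohort according to the 3+3 study design". For erlotinib it then adds: "Patients who require an erlotinib dose reduction prior to completing 1 cycle of treatment will not be evaluable for toxicity and may be replaced". The synopsis has the same rule: "Patients requiring a dose reduction before the end of Cycle 1 will not be evaluable for toxicity and may be replaced". Neither place makes an exception for a patient with a DLT.

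**What counts as a DLT.** One criterion in Protocol 8.3.3 is "Treatment discontinuation or dose reduction for >72 hours during the first cycle as a result of treatment-related toxicity". It does not say which drug's dose.

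**How DLTs are reported.** SAP 4.5 defines Enrolled, Safety and Efficacy populations and no DLT-evaluable set. A single dose of either drug puts a patient in the Safety Population (SAP 4.5.2). Table 14.3.1.8.1.1, the DLT summary, is on that population (SAP 6.1.3.1). By default, percentages are taken over everyone in the dose cohort within the named population (SAP 5.1), and nothing overrides this for DLTs. SAP 3.1 repeats the BGB324 rule for an informative patient but attaches it to no analysis set. It does not repeat the erlotinib rule.

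**The concern.** The DLT profile is an Arm A secondary objective, and it supports the recommended Phase 2 dose (RP2D) used in Arms B and C. Cohorts are of 3 to 6 patients, and Protocol 8.3.1 lets the SMC accept 3 as enough to confirm the RP2D, so one patient more or less in the denominator is visible. The escalation count and the planned table follow different rules.

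Two things can follow. The tabulated rate can be diluted by patients who were never adequately observed for a DLT. And if a patient with a DLT was set aside because of an erlotinib reduction, the study report would show the DLT but not that the escalation decision left it out. Protocol 11.3 warns of overlapping toxicities of the two drugs, so a DLT and an erlotinib reduction in the same patient is plausible.

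**Working it through.** **1. Does any exception reach the case?** Take a patient who has a Cycle 1 DLT, reduces erlotinib and stays on BGB324. Protocol 8.3.1 allows this: "Patients who experience a DLT during Cycle 1 may continue on BGB324 treatment".

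| Rule | Wording | Limited to |
|---|---|---|
| Protocol 8.3.1 (also 8.3.2) | "If a patient withdraws or is withdrawn for reasons other than DLT prior to completing Cycle 1, the patient will be replaced" | withdrawal |
| Protocol 11.7 | "for any reason other than a DLT will be replaced" | discontinuation |
| Protocol 8.3.2 (also SAP 3.1) | "unless the inability to administer BGB324 was a result of treatment-related toxicity" | missed BGB324 doses |

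This patient has not withdrawn or discontinued and need not have missed BGB324. No exception applies, so the erlotinib rule stands as written.

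**2. Who can be in the table's denominator without being evaluable?**
- Patients replaced after leaving in Cycle 1 without a DLT.
- Patients not informative under SAP 3.1.
- Patients with a Cycle 1 erlotinib reduction.
- Patients who took only erlotinib. Arm A doses it on Day -1, before any BGB324 (Protocol 10.1.2.1). The BGB324 dose is fixed at registration (Protocol 8.3.1), so such a patient can carry a cohort label.

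**3. The plan's own figures.** The plan gives no DLT rate to reproduce. Its escalation probabilities (Protocol Table 11, SAP Table 3) follow from (1-p)^3 + 3p(1-p)^5. For p = 0.30 this is 0.343 + 0.151 = 0.494, against 49% stated; for p = 0.20 it is 0.709, against 71%. The other three rows also reproduce. Table 11 is not in dispute.

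**4. Size of the mismatch.** Let d/n be the count used for escalation. Let m be the further cohort members in the Safety Population, k of them with a DLT set aside under 8.3.1.
- Planned table: (d+k)/(n+m).
- DLT-evaluable set as proposed under the fix: (d+k)/(n+k).

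The documents give neither m nor k, so these cases are illustrations.

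| Escalation count d/n | m | k | Planned table | DLT-evaluable set |
|---|---|---|---|---|
| 1/6 = 16.7% | 1 | 0 | 1/7 = 14.3% | 1/6 = 16.7% |
| 1/6 = 16.7% | 2 | 0 | 1/8 = 12.5% | 1/6 = 16.7% |
| 2/6 = 33.3% | 2 | 0 | 2/8 = 25.0% | 2/6 = 33.3% |
| 1/6 = 16.7% | 1 | 1 | 2/7 = 28.6% | 2/7 = 28.6% |
| 0/3 = 0% | 1 | 1 | 1/4 = 25.0% | 1/4 = 25.0% |
| 1/6 = 16.7% | 2 | 1 | 2/8 = 25.0% | 2/7 = 28.6% |

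With k = 0 the planned table is diluted and the new set removes the dilution. With m = k = 1 the two tables agree, and both differ from the escalation count. In the last row all three differ.

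**The case against.** **The current table hides no DLT.** This is right. A reader might infer from 8.3.1 that a DLT with an erlotinib reduction disappears from the report. It does not: the Safety Population keeps it. What is missing is any sign that it was outside the escalation count.

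**Escalation may not have been affected.** A reader might infer that the rule made escalation more permissive than Table 11 states. The documents do not support that. They give no share of DLT patients set aside, and if patients without a DLT were excluded at the same rate, the DLT rate among those counted would be unchanged. Replacement is optional, and Protocol 8.3.2 bases escalation on the safety of the combination in the first cycle, so the SMC may have counted such events. Arm A recruitment is complete and the RP2D confirmed (Protocol 8.1). No recalculated escalation probability is offered.

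**The clash with 8.3.3 is partly a matter of reading.** If the dose-reduction criterion covers erlotinib, much of the 8.3.1 rule is void, so 8.3.1 may be meant to govern as the specific rule. That narrows the overlap. It leaves a patient with a separate DLT, such as a Grade 3 event, who also reduces erlotinib.

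**A DLT-evaluable set overrides an approved rule and leans upward.** It keeps erlotinib reducers with a DLT and drops those without. This is a fair description. The reasoning is that a patient with a DLT has reached the endpoint, whereas one without needs a full Cycle 1 at the intended doses to count as event-free. The departure from 8.3.1 must be declared. Nor does the set reproduce the SMC count, which has to be shown separately.

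**The arm is small and the listings are many.** Up to about 18 patients are planned. The DLT, cohort-assignment, dosing and disposition listings (16.2.7.6, 16.2.7.8, 16.1.7.1, 16.2.5.4, 16.2.5.5, 16.2.1.1) allow partial reconstruction, and no formal analysis of safety data is planned. This lowers the severity. None of these is specified to give each patient's DLT evaluability and the reason.

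**Conclusion.** The point holds as a minor reporting weakness. The planned denominator can include patients not adequately observed for DLTs. In the single-patient illustration the dilution is 2.4 percentage points (16.7% to 14.3%); with two such patients at 2/6 it is 8.3 points (33.3% to 25.0%). Separately, no planned output would show that a DLT had been left out of the escalation count under 8.3.1.

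This assumes that the DLT table shows percentages by Arm A dose level, as the SAP 5.1 default implies, and that at least one Safety Population patient in Arm A was replaced or non-evaluable. If there was none, the rates agree. The conclusion concerns the reported DLT profile and the stated support for the RP2D. It does not show that the RP2D is wrong.

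**What to change.** Change the SAP and the study report only; the protocol need not be amended.

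1. Tabulate Arm A DLTs by dose level (Table 14.3.1.8.1.1) on a DLT-evaluable set. It comprises patients who received BGB324 and either (a) had a DLT in Cycle 1, whatever their erlotinib dose, or (b) had no DLT, completed Cycle 1, were informative under SAP 3.1 and had no Cycle 1 erlotinib reduction.
2. Keep the DLT listings on the Safety Population, so that every event stays visible.
3. Add one listing of replaced or non-evaluable Arm A patients, with the reason and any DLT.
4. Beside the table, give the count the SMC used at each dose level and the rule it applied to Cycle 1 erlotinib reductions, taken from its minutes, which Protocol 8.3.2 places in the Trial Master File.
5. Declare in SAP 5.14 that keeping DLT patients with an erlotinib reduction departs from Protocol 8.3.1. That section now reports no other changes from the protocol.

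The cost is one extra set, one re-run table and one short listing from data already collected. The DLT rate may look slightly less favourable and may differ from the SMC count; item 4 makes that difference visible.

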8.3.2 Dose escalation scheme

In Arm A, initially 3 patients will be recruited at a starting dose of 600 mg on Days 1 and 2 followed by 200 mg daily, and must complete 1 21-day cycle of treatment before a dose evaluation is made. A patient must receive all loading doses and miss no more than 3 daily doses in Cycle 1 to be considered as informative to support dose escalation, unless the inability to administer BGB324 was a result of treatment-related toxicity.

[figure not shown]
If 1 patient in a cohort experiences a DLT during Cycle 1, the cohort will be expanded to 6 patients. If 2 of 3 or 2 of 6 patients in a cohort experience DLT, no further dose-escalation will take place and the prior dose level will be nominated as the RP2D.

Safety reviews and recommendations for dose escalation or reduction will be made by the SMC. Minutes of the SMC meetings will be placed in the Trial Master File. The decision to dose escalate will be based on the safety and tolerability of BGB324 in combination with erlotinib observed in the first cycle of treatment.

If dose escalation occurs, 3 patients will be recruited at Dose Level 2 and will complete 1 cycle of treatment before a dose escalation evaluation is made, as outlined above.

Dose escalation may be stopped prior to achieving the MTD if it is considered by the Sponsor and SMC that a clinically acceptable RP2D has been achieved. If the starting dose exceeds the MTD, a lower dose, or dosing schedule (including an extended loading dose schedule) may be explored if recommended by the SMC.

If a patient withdraws or is withdrawn for reasons other than DLT prior to completing Cycle 1, the patient will be replaced for the purposes of evaluation of BGB324 dose. The operating characteristics of the 3+3 dose escalation process are summarized in Figure 8.

Figure 8 Operating Characteristics of the 3+3 Dose Escalation Process

Abbreviations: DLT=dose limiting toxicity; MTD=maximum tolerated dose

8.3.3 Assessment of DLTs

AEs will be assessed using the National Cancer Institute (NCI) CTCAE Version 4.03 (See Appendix 4) during the first cycle (21 days) of treatment in Arm A for the purposes of establishing the dose of BGB324 that can be safely given in combination with erlotinib.

DLTs will include:

- Any non-hematological toxicity \geq Grade 3, except Grade 3 nausea, vomiting or diarrhea that resolves within 72 hours with optimal therapy.
- Grade 4 thrombocytopenia or Grade 3 thrombocytopenia with bleeding.
- Grade 4 neutropenia persisting for \geq 5 days or Grade 3 or 4 febrile neutropenia.
- Treatment discontinuation or dose reduction for >72 hours during the first cycle as a result of treatment-related toxicity.

8.4 Arm B (Phase 2)

Arm B will follow a Simon-like 2-stage design with relaxed stopping for futility to evaluate the safety and tolerability, PK, PD and clinical efficacy of BGB324 in combination with erlotinib in patients with an activating EGFR mutation(s) (including exon 19 deletion or exon 21 [L858R] substitution or other rearrangement of the EGFR gene mutations) who during screening have been confirmed as T790M negative, who have progressed after receiving an approved EGFR inhibitor (i.e., prior erlotinib, afatinib, or gefitinib) and who have radiological confirmation of progressive disease. Patients who have progressed on osimertinib and fulfill all other Arm B criteria will not require testing of T790M status.

If clinical response (complete response or partial response) or disease control (stable disease) is not evident after 4 cycles of treatment in at least 1 patient among the first 9 patients enrolled, no further patients will be enrolled in Arm B. If at least 1 patient in the first 9 patients demonstrates evidence of clinical response or disease control, an additional 16 patients will be enrolled. Recruitment will continue whilst data from the first 9 patients are being analyzed. Thus, up to 25 patients are anticipated to be enrolled in Arm B.

The daily dose of erlotinib may be reduced in accordance with the erlotinib prescribing information and in line with standard practice. If a patient presents with erlotinib toxicities that warrant that they stop treatment with erlotinib, then they should be either withdrawn from the study or they may continue receiving BGB324 as a single agent until disease progression (unless unacceptable toxicity, death or withdrawal of consent).

8.5 Arm C (Phase 2)

Arm C will evaluate the safety and tolerability, PD and clinical efficacy (time to progression) of BGB324 in combination with erlotinib in the first-line setting. Eligible patients will have activating EGFR mutation(s) (including exon 19 deletion or exon 21 [L858R] substitution or other rearrangement of the EGFR gene mutations) ≥12 weeks of erlotinib without disease progression at the time of the first dose of BGB324 (Cycle 1, Day 1), with erlotinib-related toxicities well-controlled and <Grade 3.

The daily dose of erlotinib may be reduced in accordance with the erlotinib prescribing information. If a patient presents with erlotinib toxicities that warrant that they stop treatment with erlotinib, then they should be either withdrawn from the study or may continue receiving BGB324 as a single agent until disease progression (unless unacceptable toxicity, death or withdrawal of consent).

Recruitment into Arm C may be stopped if Arm B completes recruitment or is stopped before the 14 patient target is reached. Patients already enrolled into Arm C will be allowed to continue in the study in accordance with the protocol.

8.6 Overall Study Duration and Follow-Up

The study period will consist of screening, treatment and an EOS visit. The EOS visit will occur 28 days after the patient has discontinued BGB324 treatment.

8.7 Screening

Patient eligibility for the study will be determined within 28 days prior to the first dose of BGB324 (Cycle 1, Day 1). Screening assessments will be conducted according to Section 10.1.1 and Table 5.

In Arm B, the screening period may be extended to accommodate T790M confirmation from tumor biopsy. Patients who have previously been treated with a T790M inhibitor (i.e., osimertinib) and who subsequently progressed will not require T790M testing. All other assessments including scans should be conducted in the 28-day screening period.

8.8 Treatment

Eligible patients will visit the study site to receive study drug and protocol-specified procedures according to Section 10.1.2 to Section 10.1.4 and Table 5. The treatment period will consist of continuous 21-day treatment cycles.

All patients will be carefully monitored throughout Day 1 to Day 4 in Cycle 1 and will attend the clinic on Cycle 1, Day 8, Cycle 1, Day 9 and Cycle 1, Day 15 (and Day -1 in Arm A).

Patients will attend the clinic once per week (on Cycle 2, Day 1, Cycle 2, Day 8 and Cycle 2, Day 15) during Cycle 2 and then once per cycle (on Day 1) thereafter up to 12 months of

treatment (Cycle 17). Patients who remain on study after 12 months will attend the clinic every 2 cycles (6 weekly).

Patients who do not receive loading doses as assigned but are considered suitable for daily dose treatment should attend the clinic for additional ECG assessments. Twice weekly triplicate ECGs should be conducted during Cycle 1, Day 8 – Day 15 and Cycle 1, Day 15 -Day 21.

Additional visits will be scheduled for disease assessment at the end of every 2 cycles (6 weeks) cycles. The frequency of scans may be extended to the end of every 3 cycles after 12 weeks (4 cycles) and every 4 cycles after 24 weeks (8 cycles). Patients who remain on treatment for 12 months or longer may have their scans extended to a frequency of 6 months unless disease progression is suspected in which case a scan should be conducted at an earlier time point.

Patients will continue to receive BGB324 (in combination with erlotinib or as a single agent) for as long as, in the opinion of the Investigator, they continue to derive clinical benefit or until disease progression, unacceptable toxicity, death or withdrawal of consent.

In the event of erlotinib-related toxicities in Arms A, B, and C, patients may be allowed to continue receiving BGB324 as a single agent until disease progression unless unacceptable toxicity, death or withdrawal of consent. Patients who stop BGB324 treatment will be withdrawn from the study.

